#### **3.3.1 Rationale for Balovaptan and Esomeprazole Dose**

##### **3.3.1.1 Balovaptan**

A dose of 20 mg balovaptan is the highest daily dose that is currently foreseen to be used in further clinical development.

Based on previous clinical experience, single doses of balovaptan 20 mg are expected to be well tolerated. The effect of food on the plasma exposure of balovaptan has previously been shown to be small, with in particular, a reduction in  $C_{max}$ ; esomeprazole is expected to have either no effect on or to reduce the exposure of balovaptan.

##### **3.3.1.2 Esomeprazole**

The study will examine the effect of esomeprazole 40 mg on the PK of a single dose of 20 mg balovaptan. Esomeprazole is an approved medication, and the dose planned for this study, 40 mg qd, is approved for the treatment of gastric and duodenal ulcers and has an acceptable safety profile. During repeated once-daily dosing with an enteric-coated granule capsule omeprazole formulation, inhibition of acid secretion increases initially, and stabilizes within about 4 days (Olbe, 1989). The mean percentage of time with intragastric pH > 4 increases significantly after 5 days of dosing compared to after a single dose with esomeprazole 40 mg (Röhss, 2002). Intragastric pH rises to

above 4 about 1 hour to 2 hours after the morning of Day 5 (Lind, 2000). In the current study, esomeprazole 40 mg will be dosed for 4 consecutive days prior to coadministration with a single dose of balovaptan on the fifth day of esomeprazole dosing (Day 1), followed by a further single dose of esomeprazole on Day 2, to ensure that during any recirculation of balovaptan in the first 48 hours after administration, inhibition of acid production is maintained.

### **3.3.2 Rationale for Study Population**

Healthy male or female volunteers aged 18 to 65 years inclusive have been chosen as the study population due to the low risk of this study. Moreover, use of healthy subjects, as opposed to patients, will allow a clearer interpretation of the study results, as there will be no confounding factors that result from changes in disease state and/or concomitant medication use.

## **4. MATERIALS AND METHODS**

### **4.1 SUBJECTS**

The target population will be healthy male or female volunteers aged 18 to 65 years, inclusive. An attempt will be made to have 50% male and 50% female participants, and at least 30% of each sex.

Approximately 16 subjects will be enrolled, with the goal of obtaining 12 evaluable subjects. Enrolled subjects who withdraw from the study may be replaced at the discretion of the Investigator (or designee) and Sponsor to ensure adequate numbers of evaluable subjects.

#### **4.1.1 Inclusion Criteria**

Subjects must meet the following criteria for study entry:

1. Healthy male and female subjects, aged 18 to 65 years, inclusive. Healthy status is defined by absence of evidence of any active or chronic disease following a detailed medical and surgical history, a complete physical examination including vital signs, 12-lead ECGs, hematology, blood chemistry, urinalysis, and serology.
2. Body mass index (BMI) between 18 and 32 kg/m^2 inclusive, at screening.
3. For women of childbearing potential: if engaging in heterosexual activity, agreement to use at least two adequate forms of contraception during the entire study and for 90 days following the last dose of study drug. Contraceptive measures are not required for women with exclusively same-sex partners and for those for whom complete abstinence is their preferred and usual lifestyle.

- a. A woman is considered to be of childbearing potential if she is postmenarchal, has not reached a postmenopausal state (> 12 continuous months of amenorrhea with no identified cause other than menopause, confirmed with follicle-stimulating hormone (FSH)  $\geq 35$  IU/L), and has not undergone surgical sterilization (removal of ovaries and/or uterus).
  - b. The following are adequate contraceptive methods: bilateral tubal ligation; sterilization of male partner; hormonal contraceptives; hormone-releasing intrauterine devices; copper intrauterine devices; Essure.
  - c. Barrier methods alone are not considered an adequate form of contraception for this study and if utilized must be supplemented by one of the adequate methods described above. For this study barrier contraception methods are defined as: male or female condom with or without spermicide (male and female condom must not be used simultaneously); and cap, diaphragm, or sponge with spermicide.
  - d. Hormonal contraceptive methods must be supplemented by a barrier method.
4. For men: agreement to use contraceptive measures, and agreement to refrain from donating sperm, as defined below:
    - a. With female partners of childbearing potential or pregnant female partners, men must remain abstinent or use a condom during sexual activity for the entire study and for 90 days after the last dose of study drug to avoid exposing the embryo. Men must refrain from donating sperm during this same period.
  5. Able to participate, and willing to give written informed consent and to comply with the study restrictions.

#### **4.1.2 Exclusion Criteria**

Subjects who meet any of the following criteria will be excluded from study entry:

##### **Medical History**

1. Female subjects who are pregnant or lactating.
2. If female, a positive serum pregnancy test at screening or at admission.
3. Any condition or disease detected during the medical interview/physical examination that would render the subject unsuitable for the study, place the subject at undue risk or interfere with the ability of the subject to complete the study in the opinion of the Investigator.
4. In the opinion of the Investigator, any major illness within 4 weeks prior to the screening examination or any febrile illness within 1 week prior to screening.

5. History of any clinically significant, as determined by the investigator, gastrointestinal, renal, hepatic, broncho-pulmonary, neurological, psychiatric, cardiovascular, endocrinological, hematological, lymphatic, musculoskeletal, genitourinary, immunological, dermatological, or connective tissue or allergic disease, metabolic disorder, or cancer.
6. Signs and symptoms potentially indicative of peripheral neuropathy.
7. History or evidence of any medical condition potentially altering the absorption, distribution, metabolism, or elimination of drugs. Surgical history of the gastrointestinal tract affecting gastric motility or altering the gastrointestinal tract, with the exception of uncomplicated appendectomy, which is allowed.
8. A history of clinically significant in the opinion of the Investigator hypersensitivity (e.g., to drugs, including balovaptan or its excipients, esomeprazole or its ingredients, or other proton pump inhibitors, e.g., pantoprazole, lansoprazole, rabeprazole, omeprazole) or allergic reactions.
9. History or presence of clinically significant ECG abnormalities before study drug administration.
10. Subjects with screening or predose baseline mean QT interval corrected using Fridericia's formula (QTcF) >450 msec or <300 msec (using the same upper QTcF limit in both males and females).
11. Notable resting bradycardia (mean HR <40 bpm) on screening or predose baseline ECG. Notable resting tachycardia (mean HR >100 bpm) on screening or predose baseline ECG.
12. Screening or baseline ECG with evidence of clinically relevant abnormalities, e.g., atrial fibrillation, atrial flutter, complete bundle branch block, Wolf-Parkinson-White Syndrome, or cardiac pacemaker. Isolated first degree atrioventricular block or right bundle branch block will not be exclusionary.
13. Confirmed (based on the average of  $\geq 3$  consecutive measurements) systolic blood pressure greater than 139 or less than 90 mmHg, and diastolic blood pressure greater than 89 or less than 45 mmHg.
14. Clinically significant abnormalities in laboratory test results (including hepatic and renal panels, complete blood count, chemistry panel, and urinalysis). In the case of uncertain or questionable results, screening tests may be repeated to confirm eligibility. For ANC, any result below the lower limit of normal.
15. History of coagulopathies, bleeding disorders, or blood dyscrasias.
16. Current suicidal risk, in the opinion of the Investigator.
17. Subjects with unexplained syncope during the 6 months prior to screening or with presyncopal and/or syncopal symptoms during orthostatic challenge testing.
18. Current smoker or user of tobacco or nicotine-containing products or subjects who have smoked or used tobacco or nicotine-containing products within 3 months prior to first study drug administration.

19. Suspicion of or presence of a clinically relevant history of or current alcohol and/or other substance abuse or addiction.
20. Alcohol consumption of >14 units per week for males and females. One unit of alcohol equals 12 ounces of regular beer, 5 ounces of wine or 1.5 ounces of 80-proof spirits within 3 months of first dose of study drug.
21. Positive urine alcohol test or urine drug screen at screening or Day -1 of any treatment period (amphetamines [including ecstasy], barbiturates, benzodiazepines, cannabinoids, cocaine, cotinine, methadone, methamphetamines, and opiates).
22. Subjects on hormone replacement therapy if postmenopausal status cannot be ascertained from medical history or FSH levels.
23. Clinically relevant deviation from normal in the physical examination including vital signs, as determined by the investigator.
24. Positive result for HIV 1, HIV 2, hepatitis C virus antibody, or hepatitis B core (HBc) antibody. Subjects with positive antiHBc but negative hepatitis B virus surface antigen and negative hepatitis B viral DNA will be allowed.
25. Participation in an investigational drug or device study within 4 weeks or 5 times the elimination half-life, whichever is longer, prior to first dosing, or within 5 months prior to first administration of study drug in case of a study with a biological, as calculated from the day of Follow-up visit from the previous study.
26. Any donation of blood or plasma or significant blood loss within 3 months prior to screening.
27. Dietary restrictions that would prohibit the consumption of standardized meals or the high-fat, high-calorie meal planned for this study.
28. Use of any prohibited medications or food before study start or subjects who do not agree to refrain from consuming prohibited medications or food during the study.
29. Subjects likely to need concomitant medication during the study (including for dental conditions).
30. Subjects who have received any prescribed systemic or topical medication within 4 weeks (or within 5 times the elimination half-life of the medication, whichever is longer) of the first administration of study drug, unless in the opinion of the Investigator the medication will not interfere with the study procedures or compromise safety, and subjects who have received slow release medicinal formulations considered to still be active within 4 weeks (or within 5 times the elimination half-life of the medication, whichever is longer) of the first administration of study drug will also be excluded unless in the opinion of the Investigator the medication will not interfere with the study procedures or compromise safety.
31. Used the following within 7 days before the first study drug administration, unless in the opinion of the Investigator the medication will not interfere with the study procedures or compromise safety:
  - any nonprescribed systemic or topical medication
  - herbal remedies

Paracetamol (up to 4 g/day within 7 days before study drug administration and 2 g/day within 48 hours before study drug administration), dietary supplements, vitamins and minerals, hormonal contraceptives, and hormone replacement therapy are allowed.

32. Received any medications known to chronically alter drug absorption or elimination processes within 4 weeks before the first administration of study drug, unless in the opinion of the Investigator the medication will not interfere with the study procedures or compromise safety.
33. Use of any drugs or substances, including herbal treatments such as St John's wort, that are known to be substrates, inducers, or inhibitors of CYP3A4 within 4 weeks before the first administration of study drug.
34. Use of any drugs or substances, including herbal treatments, such as fluoxetine, fluvoxamine, aspirin, norethisterone, rifampicin, etc that are known to be substrates, inducers, or inhibitors of CYP2C19 within 4 weeks before the first administration of study drug.
35. Subjects under judicial supervision, guardianship, or curatorship.
36. Poor venous access for blood sampling.
37. Subjects who are intolerant to sucrose.
38. Previous exposure to balovaptan.

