## **4.2 METHOD OF TREATMENT ASSIGNMENT AND BLINDING**

This is a single-center, part-randomized, open-label, 3-treatment, 3-period crossover study. Subjects will be randomly assigned in equal proportions to one of the 2 treatment sequences according to a computer-generated randomization scheme.

After informed consent is obtained, subjects will be screened according to the inclusion and exclusion criteria. Subjects who have met all eligibility criteria will receive a randomization number on Day 1 of the first treatment period and according to the randomization code generated by the Biostatistics Department of PRA Health Sciences (PRA). Replacement subjects will receive the randomization number of the subject to be replaced, increased by a fixed unit (e.g., 1901 replacement number for randomization number 1001), and will be assigned to the same treatment sequence.

Subjects who drop out or withdraw for any reason without completing all screening evaluations successfully, will be considered "screening failures." Such subjects will not receive a randomization number, and only applicable data will be entered in the electronic case report forms (eCRFs).

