#### **4.5.1 Informed Consent Forms and Screening Log**

Written informed consent for participation in the study must be obtained before performing any study-related procedures (including screening evaluations). Informed Consent Forms for enrolled subjects and for subjects who are not subsequently enrolled will be maintained at the study site.

All screening evaluations must be completed and reviewed to confirm that subjects meet all eligibility criteria before enrollment. The Investigator or designee will maintain a screening log to record details of all subjects screened and to confirm eligibility or record reasons for screening failure, as applicable.

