##### **4.5.4.1 Orthostatic Challenge Testing**

Orthostatic challenge testing will be performed at Screening.

During a 15-minute period during which subjects will remain in a supine position, blood pressure according to the Riva-Rocci method and pulse rate will be measured after 10 and 15 minutes. If the second blood pressure measurement deviates from the previous measurement by more than 5 mmHg, another 5-minute extension period will be added, and blood pressure and pulse rate will be obtained after 20 minutes in the supine position.

The subject will then be asked to erect rapidly into a standing position, and blood pressure and pulse rate will be assessed again after 3 minutes of standing.

Standing blood pressure and pulse rates will be compared against the latest blood pressure and pulse rate values obtained in the supine position. Orthostatic hypotension is defined as a decrease in systolic blood pressure by at least 20 mmHg and/or a decrease in diastolic blood pressure by at least 10 mmHg.

Such changes used to define orthostatic hypotension or pre-syncopal/syncopal events during standing will result in exclusion.

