## Appendix 1: Schedule of Activities

	Scr	Period 1								Period 2								Period 3								F/U
	D -28 to -2	D -1	D 1	D 2	D 3 & 4	D 5	D 7	D 9	w/o	D -1	D1	D 2	D 3 & 4	D 5	D 7	D 9	D10 to D12	D 13 a	D -1 a	D 1	D 2	D 3 & 4	D 5	D 7	D 9	D16 ±2 or ET
Biochemistry	X	X				X				X				X		X			X				X			X
Urinalysis	X	X																								X
Coagulation	X	X																								X
Urine drug and alcohol screen l	X	X								X					X											
Serology	X																									
Pregnancy test m	X	X								X					X											X
FSH n	X																									
Genotyping sample		X																								
Adverse event monitoring	X	X	X	X	X	X	X	X		X	X	X	X	X	X	X	X	X	X	X	X	X	X	X	X	X

ET=early termination; F/U= follow-up; FSH=follicle-stimulating hormone; w/o=washout

- Day 13 of Period 2 is Day -1 of Period 3.
- Balovaptan will be administered following a high-fat, high-calorie meal (Treatment A) or after a ≥ 10 h fast (Treatments B and C). Subjects should fast for 4 hours after balovaptan administration and refrain from drinking for 1 hour prior to and 1 hour post dose.
- Esomeprazole will be administered 1 hour prior to balovaptan.
- Standardized meals will be provided at approximately 4 and 8 hours post-balovaptan dosing in each treatment period
- Samples at predose, and at 0.25, 0.5, 1, 1.5, 2, 2.5, 3, 3.5, 4, 5, 6, 8, 12, 16, 24, 36, 48, 72, 96, 144, and 192 hours post dose
- Samples at predose, 0.25, 0.5, 1, 1.5, 2, 3, 4, 6, 8 hours post dose of esomeprazole
- Height, weight, and BMI calculation at screening; only weight at all follow-up.
- Safety ECG will be performed in triplicate at Screening and on Day -1 of each period; at all other time points single ECGs will be performed.
- Body temperature and respiratory rate will be measured at Screening and Day -1 of each period only.
- Orthostatic challenge testing will be performed at screening.
- On Day 1, vital signs measurements will be performed at 1 hour post dose.
- Drugs of abuse (amphetamines [including ecstasy], barbiturates, benzodiazepines, cannabinoids, cocaine, cotinine, opiates, methamphetamines, and methadone).
- Serum pregnancy test performed on all female subjects at Screening and Day -1 of each treatment period (Day 13 of Period 2 is Day -1 of Period 3) and at follow-up.
- In postmenopausal women to confirm menopause

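### Do exclusion criteria 17 and 13 leave the blood-pressure screening rules incomplete or contradictory?

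*Combined protocol and SAP*

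**What the plan says.** Two screening rules are involved. Each numbered criterion appears with the same wording in the synopsis and in Section 4.1.2.

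**Orthostatic test.** Criterion 17 is the only numbered criterion that names the test: "Subjects with unexplained syncope during the 6 months prior to screening or with presyncopal and/or syncopal symptoms during orthostatic challenge testing". Section 4.5.4.1 describes the procedure, defines orthostatic hypotension as "a decrease in systolic blood pressure by at least 20 mmHg and/or a decrease in diastolic blood pressure by at least 10 mmHg", and then gives the consequence: "Such changes used to define orthostatic hypotension or pre-syncopal/syncopal events during standing will result in exclusion". The footnote in Appendix 1 gives only the timing: "Orthostatic challenge testing will be performed at screening".

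**Resting blood pressure.** Criterion 13 applies to the confirmed average of at least three measurements and sets limits of "systolic blood pressure greater than 139 or less than 90 mmHg, and diastolic blood pressure greater than 89 or less than 45 mmHg".

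**How eligibility is confirmed.** Under Section 4.2, "subjects will be screened according to the inclusion and exclusion criteria". Section 4.5.1 adds: "All screening evaluations must be completed and reviewed to confirm that subjects meet all eligibility criteria before enrollment".

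**The concern.** On the orthostatic test, Section 4.5.4.1 gives two grounds for exclusion, a qualifying fall or symptoms, while the numbered criterion gives only symptoms. Section 4.2 directs screening to the numbered criteria. A worksheet built from that list alone could therefore omit the fall, and a volunteer whose pressure drops without symptoms might be enrolled.

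On resting pressure, criterion 13 uses *or* within each pressure and *and* between the two. Taken literally, its limits apply only when both pressures are out of range, so a reading such as 150/80 mmHg would not meet it.

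At stake is the safety screening of healthy volunteers who, as Section 1.3 says, gain no health benefit. There is also a smaller analysis issue: Section 6.6 removes subjects who significantly violate the eligibility criteria from the PK population, so it should be clear what a violation is.

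**Working it through.** The protocol states no figure on this point, so the check sets the rules side by side and counts the outcomes on which they could differ.

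**Step 1: orthostatic test.** Cross a qualifying fall (yes/no) with symptoms (yes/no), which gives 2 × 2 = 4 outcomes.

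| Fall | Symptoms | Section 4.5.4.1 | Criterion 17 |
|---|---|---|---|
| yes | yes | excludes | excludes |
| no | yes | excludes | excludes |
| yes | no | excludes | silent |
| no | no | does not exclude | does not exclude |

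Section 4.5.4.1 excludes 3 and criterion 17 lists 2, so the difference is 3 − 2 = 1: the fall without symptoms (for example, a fall of 25/5 or 10/12 mmHg).

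**Step 2: is that one outcome a conflict?** Criterion 17 does not say that symptoms are the only ground, or that a symptom-free fall is acceptable. Both texts can be followed at once, and doing so excludes the volunteer. Section 4.5.1 requires every screening evaluation, not only the numbered list, to be completed and reviewed before enrolment. The orthostatic test is a screening evaluation, and the section that staff need in order to run it and judge the fall also gives the exclusion. Section 4.5.4.1 sits under Vital Signs, so criterion 23 (clinically relevant deviations, vital signs included, on investigator judgement) can reach such a fall as well. It is discretionary, so it supplements the 20/10 mmHg rule and does not replace it.

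**Step 3: criterion 13.** Systolic (<90, 90–139, >139) by diastolic (<45, 45–89, >89) gives 3 × 3 = 9 cells.

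- Drop systolic <90 with diastolic >89, which needs a pulse pressure below 1 mmHg: 9 − 1 = 8.
- Drop the cell with both in range: 8 − 1 = 7 cells with at least one pressure out.
- Both out (low/low, high/low, high/high): 3 cells, excluded on either reading.
- Exactly one out: 7 − 3 = 4 cells, excluded by the numeric limits only if either pressure is enough.

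| Reading (mmHg) | Either enough | Both needed |
|---|---|---|
| 150/80 | excluded | not by no. 13 |
| 120/95 | excluded | not by no. 13 |
| 85/60 | excluded | not by no. 13 |
| 110/40 | excluded | not by no. 13 |
| 150/95 | excluded | excluded |
| 120/80 | not excluded | not excluded |

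**Step 4: which reading would be used?** The list-type *and* occurs elsewhere in the criteria. Criterion 30 uses it to add a second excluded group, with an explicit marker: "of the first administration of study drug will also be excluded unless in the opinion of the Investigator". Criterion 20 uses a distributive *and* for males and females with no marker, though in a simpler phrase. A reader would sensibly take criterion 13 as two sets of limits, each of which applies. If not, the four cells in dispute still fall under inclusion criterion 1 (healthy status, vital signs included) and exclusion criteria 3 and 23.

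**The case for a change.** The strongest case for acting is that eligibility should be a fixed rule that can be read in one place. Section 4.1.2 excludes anyone who meets any listed criterion, and Section 9.2 allows no eligibility waivers. Section 5.7 names syncope among six event types to be reported to the FDA on an expedited basis whatever the causality, so the protocol itself takes syncope seriously. The authors also knew how to write *and/or*: they did so for the two pressure falls in Section 4.5.4.1 and for symptoms in criterion 17, but not in criterion 13. Inclusion criterion 1 and exclusion criteria 3 and 23 are general or rest on judgement, and none names the test or its thresholds. The edits would cost only a few words.

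Part of this stands. The numbered list is incomplete for the orthostatic test, and the conjunction in criterion 13 is not explicit. It would be reasonable to mention both to the sponsor as editorial points.

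The step from there to a defect does not hold. That staff would ignore Section 4.5.4.1 is a supposition about worksheets that are not in the documents, and it runs against the review duty in Section 4.5.1. Silence in criterion 17 is not a contrary answer. The study has a single center, so different sites cannot apply different readings. For the PK population, Section 6.6 already requires exclusions to be documented with reasons and decided before database lock.

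**Conclusion.** No change follows. The orthostatic point is a missing cross-reference: followed as written, the protocol already excludes the symptom-free fall. The criterion 13 point is loose wording that staff would sensibly read as a list, with other criteria covering a single out-of-range pressure on the stricter reading.

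The extent is 1 of 4 orthostatic outcomes missing from the numbered list, and 4 of 7 attainable resting-pressure combinations that depend on the reading. How many volunteers that represents cannot be derived from the documents. The plan to enrol 16 subjects for 12 evaluable, the stated confidence-interval factor of 1.11 and the food and esomeprazole comparisons do not depend on either criterion.

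This rests on two assumptions: that staff apply Section 4.5.4.1 when they review the test, as Section 4.5.1 requires, and that the general and judgement-based criteria are actually used. The intended meaning of criterion 13 remains the sponsor's to state; this conclusion does not depend on which reading was meant.

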### 3. STUDY DESIGN

#### 3.1 DESCRIPTION OF THE STUDY

This will be a single-center, part-randomized, open-label, single-dose, 3-period crossover study to investigate the effect of food and of esomeprazole on the PK of balovaptan in healthy volunteers.

Screening will be conducted between Day -28 and Day -2.

In Period 1, eligible subjects will be admitted to the clinical research unit (CRU) on Day -1 (the day prior to balovaptan dosing on Day 1) and will remain confined in the CRU until discharge on the morning of Day 5.

In Period 2, subjects will be re-admitted to the CRU on Day -1 (the day prior to balovaptan dosing on Day 1) and will remain confined in the CRU until discharge on the morning of Day 5.

In Period 3, subjects will return to the CRU for re-admission 5 days prior to administration of balovaptan (Day 9 of Period 2) to begin esomeprazole dosing. Esomeprazole will be dosed for 6 days: for 4 days prior to co-administration with balovaptan on Day 1 of Period 3, plus an additional dose on Day 2. Subjects will be discharged on Day 5.

In each period, following discharge from the CRU on Day 5, subjects will return to the CRU on Day 7 and Day 9 for further PK sampling.

There will be a washout of at least 12 days and up to 21 days between administrations of balovaptan. Thus, re-admission for Period 2 may be between 3 to 12 days after Day 9 of Period 1, and re-admission for Period 3 will be on Day 9 of Period 2.

Subjects will be randomized to 1 of 2 treatment sequences (ABC or BAC) on Day 1 of Period 1, with the treatments being as follows:

[figure not shown]
- Treatment A: 20 mg balovaptan administered as a single oral dose following consumption of high-fat, high-calorie meal
- Treatment B: 20 mg balovaptan administered as a single oral dose following a  $\geq 10$ -hour fast
- Treatment C: 40 mg esomeprazole administered once daily for 6 days and with a single oral dose of balovaptan 20 mg in the fasted state 1 hour after the fifth esomeprazole dose

During treatment periods 1 and 2, subjects will receive each of Treatment A or B, according to the randomization schedule. All subjects will receive Treatment C in Treatment Period 3.

Subjects will return for a follow-up visit on Day 16  $\pm$  2 of Period 3. Assessments during the study will be conducted according to the schedule of assessments ([Appendix 1](#)).

[Figure 1](#) presents an overview of the study design.

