#### **4.5.3 Physical Examinations**

A complete physical examination will be performed at screening and at the follow-up visit ([Appendix 1](#)). The examination should include an evaluation of the head, eyes, ears, nose, and throat; and the cardiovascular, dermatologic, musculoskeletal, respiratory, gastrointestinal, and genitourinary (at the Investigator discretion) systems. Any clinically significant abnormality identified at baseline should be recorded on the General Medical History and Baseline Conditions eCRF. Changes from baseline abnormalities should be recorded in subject notes. New or worsened clinically significant abnormalities should be recorded as adverse events on the Adverse Event eCRF and source form.

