## Appendix 1 Schedule of Activities

	Scr	Period 1								w/ o	Period 2								Period 3						F/U			
	D -28 to -2	D -1	D 1	D 2	D 3 & 4	D 5	D 7	D 9	D -1		D1	D 2	D 3 & 4	D 5	D 7	D 9	D10 to D12	D 13 a	D -1 a	D 1	D 2	D 3 & 4	D 5	D 7	D 9	D16 ±2 or ET		
Written informed consent	X									12 to 21 days between balovaptan administrations																		
Inclusion and exclusion criteria	X	X									X								X									
Demographics	X																											
Medical history	X																											
Medication history	X																											
Confinement		X	X	X	X						X	X	X	X			X	X	X	X	X	X						
Discharge						X									X								X					
Ambulatory visits							X	X							X									X	X		X	
Randomization			X																									
Balovaptan administration b			X									X								X								
Esomeprazole administration																	X	X	X c	X								
Standardized meals d			X									X							X									
PK sampling balovaptan e			X	X	X	X	X	X				X	X	X	X	X				X	X	X	X	X	X			
PK sampling esomeprazole f																			X									
Physical examination	X																										X	
Height, weight, and BMI g	X																										X	
12-lead ECG h	X	X				X									X	X							X				X	
Vital signs i	X j	X	X k			X					X	X k			X	X			X	X k			X				X	
Hematology	X	X				X					X				X	X			X				X				X	

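### Exclusion 26 counts back from screening, so a blood donation or loss between screening and first dosing (a gap of 2 to 28 days) meets no time-bound criterion

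*Combined protocol and SAP*

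**What the plan says.** Section 4.1.2 (Medical History), repeated in the synopsis, holds three look-back windows that end at screening:

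- Exclusion 26: "Any donation of blood or plasma or significant blood loss within 3 months prior to screening".
- Exclusion 4, which is left to the investigator's opinion: "any major illness within 4 weeks prior to the screening examination or any febrile illness within 1 week prior to screening".
- Exclusion 17, first clause: "Subjects with unexplained syncope during the 6 months prior to screening".

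Section 3.1 sets the timing: "Screening will be conducted between Day -28 and Day -2".

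Other criteria in the same list use a later anchor. Exclusion 18 bars those who have "used tobacco or nicotine-containing products within 3 months prior to first study drug administration". Exclusions 25 and 30 to 34 also count back from first dosing, and exclusion 20 refers to the first dose. Exclusions 2, 10, 11 and 21 name admission, the predose baseline or Day -1.

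In Appendix 1 the row "Inclusion and exclusion criteria" is marked at screening and again on Day -1 of Period 1. Hematology, biochemistry and vital signs are also marked on that Day -1. Medical history and the orthostatic test are at screening only. Section 4.5.3 says "A complete physical examination will be performed at screening and at the follow-up visit", so no repeat is scheduled before dosing. Sections 4.4.2 to 4.4.4 cover medicines, food, alcohol, exercise and fluid intake, but not blood or plasma donation.

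**The concern.** A look-back window protects the subject, and the measurements, at the time of dosing. If it closes at screening and screening can be four weeks earlier, the most recent events are the ones it misses. For donation the ordering is reversed: an older donation excludes and a newer one does not.

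The study also draws blood often, and a recent donor starts that sampling having already lost blood. What is at stake is a volunteer's safety and a consistent eligibility rule. The list gives no reason for anchoring donation to screening while tobacco, medication and prior-study windows are anchored to dosing.

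**Working it through.** **Inputs.** Screening Day -28 to Day -2 (sections 3.1 and 3.2). Day -1 is the day before Day 1, so there is no Day 0 (section 3.1). Windows are from section 4.1.2; sampling times and visits are from Appendix 1 and its footnotes.

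**1. The plan's own figure.** Section 3.2 gives screening as about 4 weeks. Days from Day -a to Day 1 with no Day 0 = 1 + a - 1 = a.

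- Day -28 to Day 1: 28 days, which agrees with 4 weeks.
- Day -2 to Day 1: 2 days.
- Day -28 to the Day -1 check: 28 - 1 = 27 days.

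The uncovered interval before first dosing is therefore 2 to 28 days. At its longest it equals the whole 4-week major-illness window and is 28 / 7 = 4 times the 1-week febrile-illness window.

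**2. A worked case for exclusion 26.** Screening is on Day -28.

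| Donation | Relative to screening | Exclusion 26 as written | If counted from first dosing |
|---|---|---|---|
| Day -40 | 12 days before | excluded | excluded (40 days before) |
| Day -10 | 18 days after | not excluded | excluded (10 days before) |

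Re-reading the criterion on Day -1 still asks about the 3 months before Day -28, so the Day -10 donor passes again.

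**3. Does anything else catch the donor?** Exclusion 3 needs a condition or disease found at interview or examination, and a donation is neither. Exclusion 14 applies only if the Day -1 laboratory result is clinically significant. No restriction in section 4.4 applies.

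**4. Illness and syncope in the same gap.** Illness still active on Day -1 fails inclusion 1 and may meet exclusion 14 or 23; temperature is taken that day. Exclusions 3 and 5 let the investigator act on a recent faint. Exclusions 30 and 31 count medication back from first dosing, so a treated illness may surface there. A resolved fever, or a faint on which the investigator does not act, triggers no automatic exclusion.

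**5. Sampling load.** 22 balovaptan time points x 3 periods = 66; plus 10 esomeprazole time points = 76 pharmacokinetic draws. Appendix 1 also marks 9 hematology time points from screening to follow-up. Draw volumes are not in the documents. At an assumed 2 to 5 mL, the pharmacokinetic draws total 76 x 2 = 152 mL to 76 x 5 = 380 mL.

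**6. Time outside the unit after first dosing, at most.** Period 1, Day 5 to Day 21: 16 days. Period 2, Day 5 to Day 9: 4 days. Period 3, Day 5 to Day 18: 13 days. Total 16 + 4 + 13 = 33 days, of which 16 + 4 + 4 = 24 precede the last pharmacokinetic sample.

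**7. Precision.** The factor in section 6.1 reproduces as exp(t(0.95; 10 df) x sqrt(ln(1 + 0.14²)) x sqrt(2/12)) = 1.109, against the stated 1.11. No eligibility window enters it.

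**The case against.** The strongest reply is that anchoring history to screening is a design choice and that Day -1 is not an empty check. Criteria are reviewed again; laboratory tests, ECG and vital signs are repeated; adverse-event questioning is scheduled; and the investigator may withdraw anyone at any time (section 4.6.2). For illness and syncope much of this stands. A reader might infer that such events in the gap are wholly unguarded. The documents do not support that, given inclusion 1 and exclusions 3, 5, 14, 23, 30 and 31. Nor do they support a firm contrast between an early fever that is barred and a late one that is admitted, because exclusion 4 itself rests on the investigator's opinion. The limit of this reply is that no repeat history or physical examination is scheduled before dosing.

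For donation the reply is weaker. Exclusion 26 has no opinion clause, and nothing else names donation. A significant bleed could sometimes be picked up through its cause or through vital signs, but a donation in a healthy volunteer would show, if at all, in the Day -1 blood count.

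The objection is also right on size. Adding whole periods (21 + 13 + 18 = 52 days) would count time in confinement; about 33 days is the correct maximum. The blood volumes are assumed, and the documents give no blood-loss limit, so no breach is shown.

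**Conclusion.** The point holds in full for exclusion 26: a donation or significant blood loss between screening and Day 1 meets no time-bound criterion. The gap is 2 to 28 days, and donation stays unrestricted through follow-up, including up to about 33 days outside the unit. For exclusions 4 and 17 the anchor is inconsistent with neighbouring criteria, but events in the gap fall to investigator judgement and Day -1 checks.

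This is a minor eligibility and safety matter. One might infer that the food or esomeprazole comparison is at risk; the documents give no mechanism or figure for that, and the sample size and the 1.11 factor are untouched. The day counts rest on the protocol's own numbering. Only the 152 to 380 mL range rests on an assumption (2 to 5 mL per draw), and the conclusion does not depend on it.

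**What to change.** - In section 4.1.2 and the synopsis, count the 3 months in exclusion 26 back from first study drug administration, the anchor exclusion 18 already uses, and ask about it at the existing Day -1 check.
- In section 4.4.4, add that subjects do not donate blood or plasma from screening to the follow-up visit. A donation during the study would then be a recordable deviation.
- Reconcile the anchors of exclusion 4 and the syncope clause of exclusion 17 with the dose-anchored criteria, or state why they differ.

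Moving an anchor also moves the far end of its window forward by the same 2 to 28 days. If the sponsor wants to keep the present reach, the wording can run from the stated time before screening up to first dosing.

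The cost is wording, one question on Day -1, and an occasional volunteer deferred or replaced. Randomization numbers are given on Day 1, so someone found ineligible on Day -1 has not yet been randomized. No visit, test or analysis is added.
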